11.5 Historical Comparator

Data collected from an FDA-funded DMD NHS will be used as a historical comparator/supplemental placebo group ([Soslow 2023](#)). The NHS utilized as a comparator is an ongoing, multi-year, multicenter study evaluating the natural progression of DMD. Eligibility is broad based on DMD diagnosis, and endpoints collected mirror endpoints collected for CPI-IFE-007 except patient-reported outcomes (PedsQL). NHS visits are scheduled yearly, and demographic, baseline characteristics, medical history, and concomitant medication information is collected at each visit along with CMR, PFTs, QMT, and accelerometry. Patients from the NHS will be selected at a 2:1 ratio (NHS to placebo) using propensity score matching (PSM) based on baselined LVEF, age, and background DMD therapy with consideration for other relevant cardiac medications (ACEi, ARB, beta-blockers, ARNI, aldosterone receptor antagonists, diuretics, calcium channel blockers. Matched NHS patients will be added to the CPI-IFE-007 placebo group from the 12-month double-blind study to create a supplemental, representative placebo group of a larger size for Month 12 efficacy analyses. For the open label extension, a historical comparator group will be formed from NHS patients selected at a 2:1 ratio (NHS to open label high-dose ifetroban) using PSM as described above. The NHS comparator group for the open label extension will be compared with open-label high-dose ifetroban patients at Month 12, Month 24, and Month 36.

11.6 Randomization

Subjects will be randomly assigned to one of three treatment groups: low-dose ifetroban, high-dose ifetroban, placebo, using a 1:1:1 randomization ratio. All subjects will be treated with IMP daily for at a minimum of six months and a maximum of 12 months.

11.7 Methods for Handling Missing Data

All missing data will be queried. Missing data which are not retrievable through queries will not be imputed. The only exception to this is one supportive analysis with missing LVEF at Month 12 imputed by LVEF at Month 6; subjects missing LVEF at both Month 6 and Month 12 will be excluded from this supportive analysis.

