8 STUDY VISITS AND PROCEDURES

8.1 Overview – Schedule of Time and Events

This clinical study will consist of a 12-week Screening Period (Week -12 to Week 0) and a 12-month Treatment Period (Month 0 to Month 12). The study visits occur on the planned dates relative to the first dose of IMP as scheduled. The visit schedule should be adhered to within the visit window indicated.

If a subject is prematurely discontinued from treatment, all assessments planned at the End of Treatment visit should be performed. Prior to all screening assessments, after discussion of participation in the study, the written consent form must be signed and dated. Although the screening assessments for this study are grouped under the heading of a single visit in this protocol, it is possible for them to be performed over more than one site visit if necessary, as long as the twelve-week screening period relative to the first dose of IMP is respected. Furthermore, the site may split the on-site study visits during the treatment period (Day 0, Month 6, Month 12 & Month 24, if applicable) into two visits no more than 7 calendar days apart provided that each of the visit days remain within the protocol established window for the on-site study visits. Subjects that fail screening for exclusion criteria, for example concomitant medications, acute illness (upper respiratory tract infection), required drug-specific discontinuation periods or laboratory tests, may be rescreened for study eligibility.

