	Week -12 to Week 0	Week -2 to Week 0	Day 0	Week 1 (\pm 2 days) Month 3,5,7,9,11 (At home) (\pm 7 days)	Month 1 (\pm 2 days) Month 3 & 9 (At home)	Month 6 (\pm 7 days)	Month 12 (\pm 7 days)	Month 15, 18 & 21 (\pm 7 days)	Month 24 (\pm 7 days)	Month 27, 30 & 33 (\pm 7 days)	Month 36 (\pm 7 days)	
Informed Consent/Accent	X											
Medical/Surgical History, Demography	X											
Screening CMR or ECHO	X ^a											
Cystatin C		X										
Research CMR			X ^a				X ^d	X		X	X	
Physical Exam, Vital Signs		X	X ^b				X	X		X	X	
Pulmonary Function Test			X				X	X		X	X	
ECG, QMT & Actigraphy			X				X	X		X	X ^h	
PROs: PedsQL, GI & NMM			X			X	X	X	X ^e	X		
CBC, CMP & Coagulation		X	X ^b				X	X		X	X	
PK Blood Sampling			X ^c	X ^c								
Urine & blood for biomarkers			X				X	X		X	X	
Review subject diary			X				X	X		X	X	
Dispense IMP			X				X					
IMP Daily Dosing			I-----Continual Once Daily Dosing-----I									
Record Concomitant Medications			I-----Continual-----I									
AE/SAE Recording (if any)			I-----Continual-----I									

a -If screening CMR follows study-specific CMR protocol and was performed within 12 weeks of Baseline visit, Baseline CMR does not need to be repeated.

b - Screening Physical Exam, Complete blood count (CBC), Comprehensive metabolic panel (CMP) & Coagulation within 2 weeks of Baseline Visit need not be repeated.

c - PK blood sampling on Day 0: pre-dose, 30, 60 (\pm 5) minutes; and 4, 8 and 24 hours (all \pm 30 minutes) post dose. Day 7 (by subject at home): pre-dose and 30, (\pm 5) minutes post-dose

d - Month 6 CMR is optional. If the Month 6 CMR is declined, a mandatory ECHO should be performed.

e - Quality of life questionnaires are to be completed at home at Month 18 only. Safety phone calls are completed at Months 15, 18 and 21.

f - The site may split on-site study visits on Day 0, Month 6, Month 12, Month 24, and Month36 into two visits no more than 7 calendar days apart provided that each of the visit days remain within the protocol established window for the on-site Study Visits.

g - If patients opt into additional 12-month open-label extension periods, each 12-month period will follow the same schedule outlined for the second 12-month open-label extension period above.

h- ECG only; QMT and actigraphy not collected following Month 24

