9 SUBJECT DISCONTINUATION AND STUDY OR SITE TERMINATION

9.1 Subject Discontinuation

Subjects will be encouraged to complete the study; however, they may voluntarily withdraw at any time. The Investigator will provide a report in the CRF describing the reason for discontinuation. If a subject withdraws before completion, every effort should be made to complete the assessments scheduled during the final scheduled assessment.

A subject may be terminated early from the study for the following reasons:

- The subject elects to withdraw consent from all future study activities, including follow-up.
- The subject is “lost to follow-up” (i.e., no further follow-up is possible because attempts to reestablish contact with the participant have failed).
- The subject dies.
- The subject develops a medical condition or is started on new medication(s) prohibited by the study or not previously mentioned in the list of prohibited medications that, in the opinion of the investigator, may pose additional risks from participation in the study, may interfere with the subject’s ability to comply with study requirements or that may impact the quality of the data obtained from the study.

Subjects who are prematurely terminated from the study will be followed to monitor safety for a minimum of 30 days or until resolution of the disqualifying event, whichever is longer, or until the Independent Safety Monitor, the CPI Director of Medical Affairs and the Principal Investigator determine that the follow-up is complete.

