## 4.2 Missing Data

For the primary endpoint and key secondary efficacy endpoints, missing data will not be imputed in the primary analyses. A supportive sensitivity analysis for the Month 12 LVEF endpoint will be conducted where missing LVEF values at Month 12 will be imputed using Month 6 values, if available. Subjects missing LVEF at both Month 6 and Month 12 will be excluded from this supportive analysis. For long-term analyses in the open-label extension, subjects missing data at key timepoints (Month 24, Month 36) will be excluded from the respective analyses. No other imputation will be provided for any endpoint.

Since LVEF is a key efficacy endpoint, the pattern of missing data will be carefully evaluated to assess potential bias. The frequency and reasons for missing LVEF measurements will be

summarized by treatment group to determine whether missingness might be related to treatment or disease progression. If systematic differences in missing data patterns are identified between treatment groups, additional sensitivity analyses may be conducted using multiple imputation methods that account for the potential relationship between the likelihood of missing data and the unobserved outcomes. This would involve creating multiple complete datasets based on observed covariates and outcomes, analyzing each dataset, and combining results according to Rubin's rules. These additional analyses would be considered exploratory and would be used to evaluate the robustness of the primary analysis approach.

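### The supportive Month 12 LVEF analysis admits only a Month 6 substitute, so it can pass over a nearer early End of Treatment CMR, and the plan never says how that scan is to be used

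*Protocol*

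**What the plan says.** **The imputation rule.** Protocol 11.7 rules out imputation, with one exemption: "The only exception to this is one supportive analysis with missing LVEF at Month 12 imputed by LVEF at Month 6". Those without either value are left out: "subjects missing LVEF at both Month 6 and Month 12 will be excluded from this supportive analysis". Protocol 11.8.3 repeats this. SAP 4.2 agrees: "missing LVEF values at Month 12 will be imputed using Month 6 values, if available", then "Subjects missing LVEF at both Month 6 and Month 12 will be excluded from this supportive analysis", and finally "No other imputation will be provided for any endpoint".

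**The scans collected.** Protocol 8.1 says that when treatment is stopped early, "all assessments planned at the End of Treatment visit should be performed". The End of Treatment visit in Protocol 8.1.2 includes a CMR. For subjects who withdraw, Protocol 9.1 is softer: "every effort should be made to complete the assessments scheduled during the final scheduled assessment". The one permitted substitute comes from a scan that need not be done. Footnote d of Protocol Table 8-1 reads: "Month 6 CMR is optional. If the Month 6 CMR is declined, a mandatory ECHO should be performed".

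**The conflicting rule.** SAP 3.3 says that the data of subjects who stop study treatment before week 52 are completed by LOCF, without limiting this to particular endpoints. SAP 4.4.4 and SAP 8 declare no departures from the protocol's analyses.

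**The concern.** The supportive analysis exists to show whether the Month 12 LVEF result depends on subjects without a Month 12 scan, many of whom will be early discontinuers. For these subjects the protocol asks for a CMR at the time of stopping. The rule does not name that scan. It names an optional scan at a fixed earlier date.

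Two things are at stake. If the rule is followed literally, the analysis may bring back few of the subjects it is meant to bring back, and would then resemble the main analysis whatever happened to them. Separately, because no passage assigns an early End of Treatment CMR to an analysis visit, two programmers could treat the same scan differently: as unused, as the last observation under SAP 3.3, or as the value of the visit at which it nominally belongs.

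**Working it through.** **1. Each type of discontinuer under each rule.** Each is assumed to have had an early End of Treatment CMR.

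| Subject | Protocol 11.7 / SAP 4.2 as written | SAP 3.3 (LOCF) |
|---|---|---|
| Stops before Month 6 | Excluded | Early scan carried forward |
| Stops between Months 6 and 12, Month 6 CMR done | Month 6 value used; nearer scan not used | Early scan carried forward |
| Stops between Months 6 and 12, Month 6 CMR declined | Excluded, if LVEF means CMR LVEF | Early scan carried forward |

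The two columns differ in every row. The condition in the third row is needed because the rule says LVEF without a modality, and a subject who declines the CMR has an ECHO. The endpoint itself (Protocol 6.5) is LVEF by CMR.

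**2. How much nearer the later scan is.** A scan at month t covers t/12 of the year; the Month 6 scan covers 6/12 = 50%. Stopping at Month 7 gives 7/12 = 58%, Month 9 gives 9/12 = 75%, and Month 10 gives 10/12 = 83%. These are shares of time. They are shares of the 12-month change only if change is linear, which is an assumption.

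**3. Planned discontinuers.** The inputs are 25% and 60 recruited (Protocol 11.1), and 10% and 54 recruited (SAP 3.4), both for a target of 48.

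- Reproducing the recruitment figures: 48 × 1.25 = 60 for the Protocol; 48 / 0.90 = 53.3, rounded up to 54, for the SAP. (Dividing by 0.75 would give 64, a separate matter.)
- Discontinuers, D = recruited × dropout rate: 60 × 0.25 = 15 (Protocol) and 54 × 0.10 = 5.4 (SAP).
- Per cell of arm by disease stage (six cells): 15 / 6 = 2.5, or 5.4 / 6 = 0.9.

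**4. Subjects excluded although an early End of Treatment CMR exists.** Let E be the share of discontinuers with that scan and M the share with a Month 6 CMR. M is limited both by uptake and by how many stop after Month 6. The documents give neither E nor M. If the two are independent (an assumption), the number is D × E × (1 − M).

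| E | M | Protocol, D = 15 | SAP, D = 5.4 |
|---|---|---|---|
| 25% | 0% | 3.8 | 1.4 |
| 25% | 50% | 1.9 | 0.7 |
| 50% | 0% | 7.5 | 2.7 |
| 50% | 50% | 3.8 | 1.4 |
| 100% | 0% | 15 | 5.4 |
| 100% | 50% | 7.5 | 2.7 |
| any | 100% | 0 | 0 |

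The end points, 0 and D, do not need the independence assumption.

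**5. Can other parts of the plan use the scan?**

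- The multiple imputation in SAP 4.2 is conditional on an observed difference in missingness between arms, and is exploratory.
- The mixed-model slopes in SAP 6.4.2 sit under the open-label extension and group subjects by double-blind and later open-label treatment. Only 12-month completers may enter the extension, so it is unclear that double-blind discontinuers are included.
- SAP 14.3.6 limits the double-blind natural-history comparison to subjects with evaluable Month 12 cardiac data.
- SAP 4.1 sends unscheduled-visit data to listings only.

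**The case against.** **A reader might infer that the early scans are discarded.** The documents do not go that far. No passage assigns the scan to a visit, so non-use is one reading. The LOCF sentence in SAP 3.3 would use it, the LVEF listing in SAP 6.2.1 would show it, and the slope models or multiple imputation might include it. What stands is that none of these is a settled, uncontradicted route into the Month 12 comparison.

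**A reader might infer that an early scan will enter the main test as a 12-month change**, since the End of Treatment visit is the Month 12 visit. The ±7-day window on the Month 12 CMR and the restriction of summary tables to scheduled visits (SAP 4.1) point the other way. They are visit-scheduling rules and not an analysis window, so one sentence is still needed.

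**A reader might infer a firm count**, for instance that the rule recovers about 4 of 15 discontinuers (15 × 0.5 × 0.5 = 3.75) where all 15 could be recovered. That needs uniform stop times, 50% Month 6 uptake and complete early-termination scanning, none of which is in the documents. It also ignores the SAP's lower dropout. The SAP's own schedule (Appendix 1) shows the Month 6 CMR with no optional footnote, so uptake may be high. Full early scanning is unlikely, because the reasons in Protocol 9.1 include death, loss to follow-up and withdrawal from all study activities. The planned six-month minimum of treatment (Protocol 11.6) argues against many early stops, though Protocol 7.2 and 9.1 provide for them.

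**Restricting the substitute to Month 6 is defensible.** In a progressive disease, a scan from Month 2 or 4 carried to Month 12 understates decline and flatters the arm that stops earlier. This stands for scans before Month 6. It does not justify preferring a Month 6 scan to a later one, since the plan already carries forward and the later scan is closer to the target date.

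**The stakes are limited.** The primary endpoint is treatment-emergent adverse events, LVEF is secondary, and SAP 4.2 leaves the main LVEF test unimputed.

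**Conclusion.** The concern holds as a gap in the missing-data rule and a contradiction within the SAP. Followed as written, Protocol 11.7 and 11.8.3 and SAP 4.2 replace a nearer CMR by an older one, or exclude a subject who has a post-baseline CMR. SAP 3.3 prescribes something different for the same subjects, and the early End of Treatment CMR has no defined analysis visit.

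Its size cannot be fixed from the documents. The number excluded despite an early-termination CMR lies between 0 and 15 at the Protocol's dropout, or between 0 and about 5 at the SAP's. Where it falls depends on Month 6 uptake, early-termination scan completion and stop times. For those who do have a Month 6 value and stop later, the cost is an older scan: 50% of the year against, for example, 75% for a stop at Month 9.

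The point affects a supportive analysis of a secondary endpoint. It is worth correcting because the correction is cheap.

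**What to change.** Before database lock, change the wording as follows.

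1. **Protocol 11.7 and 11.8.3, SAP 4.2:** in the supportive analysis, replace a missing Month 12 CMR LVEF by the latest post-baseline study CMR at or after Month 6, including an early End of Treatment CMR. Naming CMR also settles that a Month 6 ECHO value is not a substitute.
2. **A separate, labelled sensitivity version** that also uses study CMRs before Month 6, with the month of each carried-forward scan listed. Only subjects with no post-baseline study CMR are then left out.
3. **Myocardial strain:** apply the same two rules.
4. **Main test:** state that a CMR taken before the Month 12 window is not a Month 12 value.
5. **SAP 3.3:** delete the LOCF sentence, or reconcile it with SAP 4.2 and Protocol 11.7.

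The cost is protocol and SAP text and a little programming. The protocol already asks for the scans, so no procedure is added. The drawback is that carried-forward scans understate the 12-month change, most of all the early ones. The analysis should therefore stay supportive, and the version with scans before Month 6 should be read with their timing in view.

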11.8 Data Analysis Plan

11.8.1 Demographic and Baseline Characteristics

Demographic and baseline characteristics will be summarized by dose level and overall.

11.8.2 Exposure and Compliance

Exposure and compliance will be summarized for the Safety Population by dose level and overall. Comments recorded on the Study Drug Accountability CRF page will not be applied in the computation of compliance. Exposure is the duration (days) of treatment, computed as:

Exposure= Date of Final Dose- Date of Baseline Visit + 1.

Treatment compliance will be calculated as:

Compliance (%) = $100 * (\text{Total Number of Capsules Dispensed} - \text{Total Number of Capsules Returned}) / (\text{Expected Usage})$,

where Expected Usage= Exposure * number of capsules to have been taken daily (1 capsule for 50 mg, 2 for 100 mg, 3 for 150 mg, or 6 for 300 mg).

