7.2 Drugs and Dosages

Oral ifetroban is available as the sodium salt of the free acid and is for investigational use only. The drug is supplied as a capsule dosage form (size # 1, white opaque) for oral administration. Ifetroban capsules are formulated as a dry powder blend and filled into hard gelatin capsules. The formulation consists of ifetroban, mannitol, microcrystalline cellulose, crospovidone, magnesium oxide, colloidal silicon dioxide, and magnesium stearate. Capsules are filled into high density polyethylene bottles and sealed with screw-cap closures. Capsules are only available at one strength of the sodium salt, i.e., 52.5 mg corresponding to a free-acid dose of 50 mg.

Matching placebo capsules are formulated as a dry powder blend filled into capsules. The formulation consists of microcrystalline cellulose, crospovidone, colloidal silicon dioxide, and magnesium stearate. Capsules are filled into high density polyethylene bottles and sealed with screw-cap closures.

The bottles of oral ifetroban or placebo will contain the following information on the label:

PLACEBO OR IFETROBAN CAPSULES 50 MG

Quantity: 75 Capsules

Instruction: Take capsules by mouth as directed.

Store at controlled room temperature, 20°C – 25°C (68°F – 77°F)

Caution: New Drug-Limited by Federal law to investigational use

Cumberland Pharmaceuticals Inc.

Additionally, each individual bottle will be labelled with a unique numeric code that identifies the contents to the unblinded sponsor representative. Subjects will be randomized to low-dose ifetroban, high-dose ifetroban or placebo.

Low Dose: < 35 kg: 50 mg, ≥ 35 kg: 100 mg/day

High Dose: < 35 kg: 150 mg, ≥ 35 kg: 300 mg/day

Table 7-1 Ifetroban Dose Levels & Sub-Groups

DMD Sub-Group	Low Dose	High Dose	Placebo
Early Stage (LVEF > 45%)	8 subjects	8 subjects	8 subjects

DMD Sub-Group	Low Dose	High Dose	Placebo
Advance Stage (current/historical LVEF 35-45%)	8 subjects	8 subjects	8 subjects

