Should a subject experience an intolerable toxicity attributed to study drug the dose may be reduced by 50-mg decrements (one capsule) at a time at the investigator's discretion. Any subject receiving 50 mg/day who experiences an intolerable toxicity attributed to study drug will be discontinued from the study. A subject may also have their dose held for up to two weeks to allow a severe adverse event to improve or resolve before considering resuming drug. IMP may resume at the starting dose or a reduced dose at the investigator's discretion, once the toxicity has improved or resolved. Any subject with a serious toxicity that does not improve or resolve after a two week hold of IMP will be discontinued from the study.

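### Expected Usage is total exposure times one fixed capsule count, which does not fit permitted dose reductions, holds or the placebo arm; how capsule counts are masked is also unstated

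*Protocol*

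**What the plan says.** Compliance is 100 times (capsules dispensed minus capsules returned) divided by Expected Usage. Expected Usage is Exposure times the daily capsule number, which the Protocol (11.8.2) gives as "1 capsule for 50 mg, 2 for 100 mg, 3 for 150 mg, or 6 for 300 mg"; SAP 5.3 repeats the list. Exposure is the date of the final dose minus the date of the baseline visit plus 1, so days on hold are included. The numerator starts from "Total Number of Capsules Dispensed", with no split between active and placebo capsules. Both sections summarise compliance for the whole Safety Population; SAP 5.3 does so by treatment group and overall.

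Protocol 7.2 sets the dosing behind these counts:

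- Strength: "Capsules are only available at one strength of the sodium salt, i.e., 52.5 mg corresponding to a free-acid dose of 50 mg".
- Doses: "Low Dose: < 35 kg: 50 mg, ≥ 35 kg: 100 mg/day" and "High Dose: < 35 kg: 150 mg, ≥ 35 kg: 300 mg/day".
- Placebo: "Matching placebo capsules are formulated as a dry powder blend filled into capsules". No number per day is given.
- Reductions: after an intolerable toxicity "the dose may be reduced by 50-mg decrements (one capsule) at a time", at the investigator's discretion. A dose may also be held for up to two weeks.

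Bottles carry a shared placebo-or-ifetroban label and a numeric code. Neither document has a section on blinding procedures or mentions filler capsules.

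**The concern.** The multiplier is a single number per subject, but the protocol lets the daily number change during treatment. The list has no entry for 4 or 5 capsules, both reachable from 6 by one-capsule steps, and does not say what happens to the denominator after a reduction or during a hold. A subject who does exactly as told can therefore be recorded as under-compliant. For placebo the denominator is not defined at all.

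The same list raises a masking question. With one strength, the number of capsules follows the dose. Coding the bottles hides what a capsule contains, not how many are taken, and sites count pills with subjects (Protocol 8.1.2). If subjects take the listed numbers, anyone who knows the weight band can exclude one of the two active arms. The primary endpoint is reported adverse events, and lung function and PedsQL depend on effort or self-report, so knowledge of dose level could matter for them.

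**Working it through.** **Inputs.** Strength 50 mg and the four doses (Protocol 7.2); the compliance formula and counts (Protocol 11.8.2, SAP 5.3); 8 subjects per arm per disease stage (Protocol Table 7-1). A 365-day exposure, and a reduction after day 182, are assumptions made for illustration.

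**1. The stated counts reproduce.** Count = dose / 50 mg: 50/50 = 1, 100/50 = 2, 150/50 = 3, 300/50 = 6.

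**2. Reduction from 6 to c capsules, full adherence.** Capsules taken = 6 × 182 + c × 183. With the starting count, Expected Usage = 6 × 365 = 2190. With the reduced count it is c × 365.

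| c | Taken | Starting count used | Reduced count used |
|---|---|---|---|
| 5 | 1092 + 915 = 2007 | 2007/2190 = 91.6% | 2007/1825 = 110.0% |
| 4 | 1092 + 732 = 1824 | 1824/2190 = 83.3% | 1824/1460 = 124.9% |
| 3 | 1092 + 549 = 1641 | 1641/2190 = 74.9% | 1641/1095 = 149.9% |

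The true value is 100% in each row, and neither count returns it. The size depends on timing: with the starting count, the score runs from c/6 (83%, 67% or 50%) for a reduction right at the start up to nearly 100% for one at the end.

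**3. Hold of 14 days, full adherence otherwise.** 6 × 351 / (6 × 365) = 2106/2190 = 96.2%. The percentage is the same for any count, because the count cancels.

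**4. Placebo.** 8 + 8 = 16 of 48 planned subjects have no stated number of capsules per day, so their Expected Usage cannot be formed from these documents.

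**5. Capsule numbers by arm.** High to low is 3 to 1 below 35 kg and 6 to 2 at or above 35 kg, threefold in both bands. Two cases follow.

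- *Listed counts are taken.* Dose level shows in the number of capsules. Over 182 days in bottles of 75, low versus high needs 3 vs 8 bottles (182/75 = 2.4; 546/75 = 7.3) or 5 vs 15 (364/75 = 4.9; 1092/75 = 14.6). If placebo subjects in a band are split across both counts, neither count separates active from placebo. If they all take one count, the other count identifies active drug.
- *Counts are equalised with placebo capsules at the high-dose number.* A fully adherent low-dose subject scores 3/1 or 6/2 = 300%, one taking 80% scores 240%, and one taking a third scores 100%. The high-dose arm still scores correctly.

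**6. Day-by-day sum.** For the subject reduced from 6 to 5, Expected Usage = 6 × 182 + 5 × 183 = 2007 and compliance = 2007/2007 = 100%. Days on hold add zero.

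**The case against.** The strongest reply is that the sections agree with one another: one strength, counts equal to dose over 50 mg, reductions of one capsule. The operative term in the formula is the number of capsules that should have been taken daily, and the parenthesis may only convert the four starting doses. On that reading a reduced count or a placebo count could be supplied in the programming specifications, which SAP section 10 places in separate documents. Reductions also require an intolerable toxicity and may be few.

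Part of this stands. A reader might infer that one of the sections must be wrong. The documents do not support that: calling the trial double-blind conflicts with visible dose level only if it promises to mask dose as well as active versus placebo, and no section says so. A reader might also take 300% as an error present in this plan. It needs filler capsules that no section describes, and equating one capsule with 50 mg reads against them. Counting only active capsules through the bottle codes could also rescue the active arms, but neither document says that this will be done.

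Nor is it established that Per Protocol membership is affected. The rule on more than 20% of prescribed doses missed applies between visits and is not expressly tied to this cumulative percentage. The argument about bias has limits too: the between-arm tests in Protocol 11.8.3 are on LVEF and myocardial strain from imaging, and the effort-dependent and self-reported endpoints of the double-blind period are only summarised there.

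What the reply does not answer is the formula itself. Exposure times any one count is wrong for a subject whose count changed, and the fixed list does not say which count to use.

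**Conclusion.** The point holds for the compliance rule. As written it misstates compliance after a reduction or a hold that the protocol allows: about 92%, 83% or 75% instead of 100% for a mid-year drop from 6 to 5, 4 or 3 capsules if the starting count is used, and 96% for a two-week hold. It also leaves placebo without a denominator. The percentages rest on a 365-day exposure, full adherence and the assumed timing. How many subjects would be affected cannot be told from the documents.

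On masking, the conclusion is conditional. Either dose level is visible through a threefold difference in capsule number, with active versus placebo possibly still masked, or counts are equalised and the formula overstates low-dose compliance threefold. The documents do not show which case applies, so neither unblinding of active versus placebo nor a 300% score should be stated as fact.

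**What to change.** In Protocol 11.8.2 and SAP 5.3, define Expected Usage as the sum over days of all capsules, active plus any placebo, assigned to that subject on that day. Let permitted reductions change the daily number and hold days count as zero, and apply the rule to all three arms.

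Reconcile Protocol 7.2 (strength, doses, reductions and holds) with Protocol 11.8.2 and SAP 5.3 by stating capsules per day for each arm and weight band, including placebo, and whether and how the number is masked. If counts do differ by arm, say that the trial is not blinded to dose level.

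The cost is a clarification in both documents before database lock, plus a programming change. No new assessments are needed if the dates of dose changes and holds are already recorded. That should be confirmed, because both sections exclude comments on the drug accountability page from the calculation.
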